## PROTOCOL SYNOPSIS

**Gilead Sciences, Inc.**  
**[name]**  
**[name], USA**

[figure not shown]
---

Study Title:	A Phase 3, Randomized, Controlled Study Evaluating the Efficacy and Safety of Idelalisib (GS-1101) in Combination with Ofatumumab for Previously Treated Chronic Lymphocytic Leukemia
Study Centers Planned:	Approximately 115 centers in the United States, Canada, Australia, and Europe
IND Number:	101254
EudraCT Number:	2012-001236-65
Primary Objective:	

• To evaluate the effect of the addition of idelalisib (GS-1101) to ofatumumab on progression-free survival (PFS) in subjects with previously treated chronic lymphocytic leukemia (CLL)

Secondary Objectives:	

• To evaluate the effect of the addition of idelalisib to ofatumumab on the onset, magnitude, and duration of tumor control

• To evaluate the effect of the addition of idelalisib to ofatumumab on the onset, magnitude, and duration of tumor control for subjects with 17p deletion and/or TP53 mutation

• To assess the effect of the addition of idelalisib to ofatumumab on measures of subject well-being, including overall survival (OS), health-related quality of life (HRQL) and performance status

• To assess the effects of the addition of idelalisib to ofatumumab on disease-associated biomarkers and to evaluate potential mechanisms of resistance to idelalisib

• To characterize the effect of ofatumumab on idelalisib exposure through evaluation of idelalisib plasma concentrations over time

• To describe the safety profile observed with the addition of idelalisib to ofatumumab

• To estimate health resource utilization associated with the addition of idelalisib to ofatumumab

---

**Study Design:** Study GS-US-312-0119 is a Phase 3, multicenter, 2-arm, randomized, controlled, parallel-group, clinical trial.

### Study Schema

### Treatment Groups

- Arm A: idelalisib + ofatumumab (1000-mg dosing regimen)
- Arm B: Ofatumumab (2000-mg dosing regimen)

### Randomization and Stratification

- 2:1 allocation to Arm A vs Arm B with implementation through an interactive web response system (IWRS)
- Fixed-block centralized randomization with allocation of subjects within the 8 strata as defined by the intersection of 3 binary stratification factors:
- 17p deletion and/or TP53 mutation in CLL cells: either vs neither (or indeterminate)
- Immunoglobulin heavy chain variable region (IgHV) mutation: unmutated (or IgHV3-21) vs mutated (or indeterminate)
- Disease status: refractory (CLL progression < 6 months from completion of prior therapy) vs relapsed (CLL progression ≥6 months from completion of prior therapy)

Number of  
Subjects  
Planned:

Total of ~255 subjects (~170 subjects in Arm A and ~85 subjects in Arm B)

Target Population:	
The target population comprises adults with previously treated CLL who have measurable lymphadenopathy, require treatment for CLL, have disease that is not refractory to ofatumumab, and might benefit from a change in therapy because they have experienced CLL progression < 24 months since the completion of the last prior treatment.

Duration of Treatment:	
Idelalisib will be taken continuously until the earliest of subject withdrawal from study, definitive progression of CLL, intolerable study drug-related toxicity, pregnancy, substantial noncompliance with study procedures, or study discontinuation. Idelalisib administration should be continued in subjects with a positive benefit-risk profile assessment as per the investigator.
 
Ofatumumab will be administered until the earliest of a maximum of 12 infusions, subject withdrawal from study, definitive progression of CLL, intolerable ofatumumab-related toxicity, pregnancy, substantial noncompliance with study procedures, or study discontinuation.
 
Subjects in Arm A will continue with idelalisib or ofatumumab, even if the other drug must be discontinued due to toxicity.

Diagnosis and Main Eligibility Criteria:	
Inclusion Criteria
 
Subjects must meet all of the following inclusion criteria to be eligible for participation in this study:
 

1) Male or female <math>\geq 18</math> years of age.

2) Diagnosis of B-cell CLL, with diagnosis established according to International Workshop on Chronic Lymphocytic Leukemia (IWCLL) criteria and documented within medical records.

3) CLL that warrants treatment (consistent with accepted IWCLL criteria for initiation of therapy). Any of the following conditions constitute CLL that warrants treatment:

a) Evidence of progressive marrow failure as manifested by the onset or worsening of anemia and/or thrombocytopenia, or

b) Massive (ie, lower edge of spleen <math>\geq 6</math> cm below the left costal margin), progressive, or symptomatic splenomegaly, or

c) Massive (ie, <math>\geq 10</math> cm in the longest diameter), progressive, or symptomatic lymphadenopathy, or

d) Progressive lymphocytosis in the absence of infection, with an increase in blood absolute lymphocyte count (ALC) <math>\geq 50\%</math> over a 2-month period or lymphocyte doubling time of < 6 months (as long as initial ALC was <math>\geq 30,000/L</math>), or

- e) Autoimmune anemia and/or thrombocytopenia that is poorly responsive to corticosteroids or other standard therapy, or
- f) Constitutional symptoms, defined as any one or more of the following disease-related symptoms or signs occurring in the absence of evidence of infection:
  - i) Unintentional weight loss of  $\geq 10\%$  within the previous 6 months, or
  - ii) Significant fatigue ( $\geq$  Grade 2), or
  - iii) Fevers  $> 100.5$  °F or  $38.0$  °C for  $\geq 2$  weeks, or
  - iv) Night sweats for  $>1$  month
- 4) Presence of measurable lymphadenopathy (defined as the presence of  $\geq 1$  nodal lesion that measures  $\geq 2.0$  cm in the longest diameter [LD] and  $\geq 1.0$  cm in the longest perpendicular diameter [LPD] as assessed by computed tomography [CT] or magnetic resonance imaging [MRI]).
- 5) Prior treatment for CLL comprising therapy with either of the following types of drugs given alone or in combination:
  - a) A purine analog (eg, fludarabine, pentostatin, cladribine) administered for  $\geq 2$  cycles of cytotoxic treatment
  - b) Bendamustine administered for  $\geq 2$  cycles of treatment

***Note: Prior drugs may have been administered as single agents or as components of combination therapies. Subjects may also have received other commercially available therapies (eg, rituximab, alemtuzumab, ofatumumab, lenalidomide, corticosteroids, or others) or non-excluded investigational therapies. Each repeated but separated therapeutic application of the same single-agent or combination is considered an independent regimen.***

- 6) Documentation of CLL progression  $< 24$  months since the completion of the last prior therapy for CLL.
- 7) Discontinuation of all therapy (including radiotherapy, chemotherapy, immunotherapy, or investigational therapy) for the treatment of CLL  $\geq 6$  weeks before randomization.  
Note: Subjects may be receiving corticosteroids to manage CLL manifestations.
- 8) All acute toxic effects of any prior antitumor therapy resolved to Grade  $\leq 1$  before randomization (with the exception of alopecia [Grade 1 or 2 permitted], neurotoxicity [Grade 1 or 2 permitted], or bone marrow parameters Grade 1, 2, 3, or 4 permitted]).

- 9) Karnofsky performance score of  $\geq 60$ .
- 10) Required baseline laboratory data (within 4 weeks prior to randomization) as shown in the table below.  
*Note: Confirmation should be considered for out-of-range values to determine if the abnormality is real or artifactual. Values should be obtained within the screening period and should generally be the most recent measurement obtained. Subjects with any degree of neutropenia, thrombocytopenia, or anemia due to CLL or prior therapy may enroll.*

**Required Screening Laboratory Values**

Organ System	Parameter	Required Value
Hepatic	Serum total bilirubin	$\leq 1.5 \times \text{ULN}$ (unless elevated due to Gilbert syndrome or hemolysis)
	Serum ALT	$\leq 2.5 \times \text{ULN}$
	Serum AST	
Renal	eC Cr a	$> 30 \text{ ml/min}$
Pregnancy	$\beta\text{-HCG}^b$	Negative
Infection	HIV	Negative HIV antibody
	HBV	Negative HBsAg and negative HBc antibody or positive HBc and negative for HBV DNA by quantitative PCR
	HCV	Negative viral RNA (if HCV antibody is positive)

a As calculated by the Cockcroft-Gault formula {Cockcroft 1976} (see Appendix 5)  
 b For women of child-bearing potential only; serum  $\beta\text{-HCG}$  must be negative during screening and serum  $\beta\text{-HCG}$  or urine dipstick pregnancy test must be negative at randomization (Visit 2)  
**Abbreviations:**  $\beta\text{-HCG}$ = beta human chorionic gonadotropin, ALT=alanine aminotransferase, AST=aspartate aminotransferase, DNA=deoxyribonucleic acid, eCCr=estimated creatinine clearance, HBc antibody=anti-hepatitis B core antibody, HBsAg=hepatitis B surface antigen, HBV=hepatitis B virus, HCV=hepatitis C virus, HIV=human immunodeficiency virus, Ig=immunoglobulin, PCR=polymerase chain reaction, RNA=ribonucleic acid, ULN=upper limit of normal

- 11) For female subjects of child-bearing potential, willingness to use a protocol-recommended method of contraception from the screening visit (Visit 1) throughout the study treatment period and to 30 days from the last dose of study drug or 12 months from the last dose of ofatumumab (whichever is later). Note: A female subject is considered to be of child-bearing potential unless she has had a hysterectomy, bilateral tubal ligation, or bilateral oophorectomy; has medically documented ovarian failure (with serum estradiol and follicle-stimulating hormone [FSH] levels within the institutional postmenopausal range and a negative serum or urine  $\beta\text{HCG}$ ); or is menopausal (age  $\geq 54$  years with amenorrhea for  $\geq 6$  months).

- 12) For male subjects of child-bearing potential having intercourse with females of child-bearing potential, willingness to use a protocol-recommended method of contraception from the randomization visit (Visit 2) throughout the study and for 90 days following the last dose of study drug and to refrain from sperm donation from randomization (Visit 2) throughout the study and for 90 days following the last dose of study drug. Note: A male subject is considered able to father a child unless he has had a bilateral vasectomy with documented aspermia or a bilateral orchiectomy, or has ongoing testicular suppression with a depot luteinizing hormone-releasing hormone (LH-RH) agonist (eg, goserelin acetate [Zoladex®]), leuprolide acetate [Lupron®]), or triptorelin pamoate [Trelstar®]).
- 13) In the judgment of the investigator, participation in the protocol offers an acceptable benefit-to-risk ratio when considering current CLL disease status, medical condition, and the potential benefits and risks of alternative treatments for CLL.
- 14) Willingness and ability to comply with scheduled visits, drug administration plan, imaging studies, laboratory tests, other study procedures, and study restrictions. Note: Psychological, social, familial, or geographical factors that might preclude adequate study participation should be considered.
- 15) Evidence of a personally signed informed consent indicating that the subject is aware of the neoplastic nature of the disease and has been informed of the procedures to be followed, the experimental nature of the therapy, alternatives, potential benefits, possible side effects, potential risks and discomforts, and other pertinent aspects of study participation.

#### Exclusion Criteria

Subjects who meet any of the following exclusion criteria are not to be enrolled in this study:

- 1) Known histological transformation from CLL to an aggressive lymphoma (ie, Richter transformation). **Note: *Biopsy documentation of the absence or presence of transformation is not required.***
- 2) Known presence of intermediate- or high-grade myelodysplastic syndrome (ie, subjects are excluded who have  $\geq 5\%$  bone marrow blasts; karyotypic abnormalities other than normal, Y deletion, 5q deletion, or 20q deletion; or  $\geq 2$  lineages of cytopenias due to myelodysplasia).

- 3) History of a non-CLL malignancy except for the following:  
adequately treated local basal cell or squamous cell carcinoma of the skin, cervical carcinoma in situ, superficial bladder cancer, asymptomatic prostate cancer without known metastatic disease and with no requirement for therapy or requiring only hormonal therapy and with normal prostate-specific antigen for  $\geq 1$  year prior to randomization, other adequately treated Stage 1 or 2 cancer currently in complete remission, or any other cancer that has been in complete remission for  $\geq 2$  years.
- 4) Known hypersensitivity or intolerance to any of the active substances or excipients in the formulations for either idelalisib or ofatumumab.
- 5) Evidence of ongoing systemic bacterial, fungal, or viral infection at the time of randomization (Visit 2). ***Note: Subjects with localized fungal infections of skin or nails are eligible. Subjects may be receiving prophylactic antiviral or antibacterial therapies at the discretion of the investigator; anti-pneumocystis prophylaxis is encouraged. For subjects who are at substantial risk of an infection (eg, influenza) that may be prevented by immunization, consideration should be given to providing the vaccine prior to initiation of protocol therapy.***
- 6) Ongoing drug-induced liver injury, chronic active hepatitis C (HCV), chronic active hepatitis B (HBV), alcoholic liver disease, non-alcoholic steatohepatitis, primary biliary cirrhosis, extrahepatic obstruction caused by cholelithiasis, cirrhosis of the liver, or portal hypertension.
- 7) Ongoing drug-induced pneumonitis.
- 8) Ongoing inflammatory bowel disease.
- 9) Ongoing alcohol or drug addiction.
- 10) Pregnancy or breastfeeding.
- 11) History of prior allogeneic bone marrow progenitor cell or solid organ transplantation.
- 12) Ongoing immunosuppressive therapy other than corticosteroids. ***Note: Subjects may use topical, enteric, inhaled, or systemic corticosteroids as therapy for manifestations of CLL, comorbid conditions, or autoimmune anemia and/or thrombocytopenia. During study participation, subjects may receive systemic or other corticosteroids as pretreatment for ofatumumab infusions or as needed for treatment-emergent comorbid conditions.***

- 13) In a subject with a history of prior ofatumumab therapy, the time from the last dose of ofatumumab to documented CLL progression is < 6 months.
- 14) History of prior therapy with any inhibitor of AKT, Bruton tyrosine kinase (BTK), Janus kinase (JAK), mammalian target of rapamycin (mTOR), phosphatidylinositol 3-kinase (PI3K) (including idelalisib), or spleen tyrosine kinase (SYK).
- 15) Prior participation in an idelalisib clinical trial.
- 16) Concurrent participation in another therapeutic clinical trial.
- 17) Prior or ongoing clinically significant illness, medical condition, surgical history, physical finding, electrocardiogram (ECG) finding, or laboratory abnormality that, in the investigator's opinion, could adversely affect the safety of the subject or impair the assessment of study results.

Study  
Procedures/  
Frequency:

Subjects will be randomized with a 2:1 ratio into Arm A or Arm B of the study. In Arm A, subjects will take idelalisib orally BID continuously and will receive 12 infusions of ofatumumab over ~24 weeks. In Arm B, subjects will receive 12 infusions of ofatumumab over ~24 weeks.

Clinic/laboratory visits will occur weekly for Weeks 1 through 8, every 4 weeks at Weeks 12, 16, 20, and 24, and every 6 weeks between Weeks 24 and 48. Subjects continuing on study drug(s) past Week 48 will have clinic visits every 12 weeks. Subjects will be assessed for safety at each visit. Subjects in Arm A will require monthly CMV testing. Subjects will be assessed for CLL disease status by physical and/or laboratory examinations at each visit and by CT or MRI at Weeks 8, 16, 24, 36, 48 and every 12 weeks thereafter until the primary endpoint is met.

---

**Test Therapy, Dose,  
and Mode of  
Administration:**

- Arm A: Idelalisib: 150 mg taken orally BID starting on Day 1 and administered continuously thereafter

---

**Study Drug, Dose,  
and Mode of  
Administration:**

- Arm A: Ofatumumab: 300 mg intravenously on Day 1 (Week 1); thereafter 1,000 mg intravenously on Day 8 (Week 2), Day 15 (Week 3), Day 22 (Week 4), Day 29 (Week 5), Day 36 (Week 6), Day 43 (Week 7), Day 50 (Week 8), Day 78 (Week 12), Day 106 (Week 16), Day 134 (Week 20), Day 162 (Week 24) (for a total of 12 infusions)

- Arm B: Ofatumumab: 300 mg intravenously on Day 1 (Week 1); thereafter 2,000 mg intravenously on Day 8 (Week 2), Day 15 (Week 3), Day 22 (Week 4), Day 29 (Week 5), Day 36 (Week 6), Day 43 (Week 7), Day 50 (Week 8), Day 78 (Week 12), Day 106 (Week 16), Day 134 (Week 20), Day 162 (Week 24) (for a total of 12 infusions)

**Criteria for Evaluation:**

Primary Endpoint

- Progression-free survival (PFS) – defined as the interval from randomization to the earlier of the first documentation of definitive disease progression or death from any cause; definitive disease progression is CLL progression based on standard criteria, other than lymphocytosis alone

Secondary and Exploratory Endpoints

- Five endpoints are designated as secondary endpoints for which sequential testing will be performed to control Type I error rate. Secondary endpoints will be ORR, lymph node response rate, OS, PFS in the subgroup of 17p deleted and/or TP53 mutated subjects, and CR rate. All other endpoints will be considered exploratory.

*Tumor Control*

- Overall response rate (ORR) – defined as the proportion of subjects who achieve a complete response (CR) or partial response (PR) response for at least 8 weeks
- Lymph node response rate – defined as the proportion of subjects who achieve a  $\geq 50\%$  decrease from baseline in the sum of the products of the greatest perpendicular diameters (SPD) of index lesions
- PFS in the subgroup of subjects with 17p deletion and/or TP53 mutation
- CR rate – defined as the proportion of subjects who achieve a confirmed CR

■ [REDACTED]

■ [REDACTED]

■ [REDACTED]

[REDACTED]

[REDACTED]

[REDACTED]

[REDACTED]

[REDACTED]

[REDACTED]

[REDACTED]

*Patient Well-Being*

- Overall survival (OS) – defined as the interval from randomization to death from any cause

[REDACTED]

[REDACTED]

*Pharmacodynamic Markers of Drug Activity and Resistance*

[REDACTED]

*Exposure*

[REDACTED]

*Safety*

[REDACTED]

*Pharmacoeconomics*

[REDACTED]

---

**Statistical Methods:** Analysis Methods

Appropriate data analysis sets will be defined. The intent-to-treat (ITT) analysis set will be used in the analyses of the primary efficacy endpoint, PFS. The ITT analysis set will include data from all subjects who are randomized, with study drug assignment designated according to initial randomization, regardless of whether subjects receive any study drug(s) or receive a different regimen from that to which they were randomized. A safety analysis set will comprise data from subjects who receive  $\geq 1$  dose of study drug, with treatment assignment designated according to the actual study drug(s) received. Other analysis sets [per-protocol (PP) and pharmacodynamic/pharmacokinetic analysis sets] will be used for certain analyses as well.

Subject characteristics and study results will be described and summarized by treatment arm and assessment for the relevant analysis sets. Descriptive summaries will be prepared to show sample size, mean, standard deviation, 95% confidence intervals (CIs) on the mean, median, minimum, and maximum for continuous variables and counts, percentages, and 95% CIs on the percentage for categorical variables.

An independent review committee (IRC) will review radiographic data and pertinent clinical data in order to provide expert evaluation of tumor status. The findings of the IRC will be considered primary for analyses of PFS and other tumor control endpoints.

For the primary efficacy analysis, the difference in PFS between the treatment arms will be assessed in the ITT analysis set using Kaplan-Meier methods and the stratified log-rank test. Medians, ranges, the proportions of subjects who are progression-free at 24 and 48 weeks from randomization (based on Kaplan-Meier estimates), hazard ratios, and the corresponding 95% CIs (as calculated using a Cox proportional hazards regression model) will be presented.

Secondary endpoints will be ORR, lymph node response rate, OS, PFS in the subgroup of subjects with 17p deletion and/or TP53 mutation, and CR rate. The primary efficacy hypothesis relating to PFS must be rejected at the pre-specified significance level before the efficacy hypotheses for these secondary efficacy endpoints are tested. These 5 secondary endpoints will be tested at the 2-sided 0.03 significance level in the order listed at an interim or final analysis when the primary endpoint is rejected. If a null hypothesis is not rejected, formal sequential testing will be stopped and only nominal significance will be cited for the remaining secondary endpoints.

For secondary or exploratory endpoints relating to tumor control, patient well-being, and biomarkers, analyses will be done based on the ITT, PP, or pharmacodynamic data sets, as appropriate. Time-to-event efficacy endpoints will be analyzed in a similar manner as PFS. Categorical variables will be compared using the Cochran Mantel-Haenszel test adjusted for stratification factors. Continuous endpoints will be assessed using analysis of covariance (ANCOVA) with baseline values and stratification factors as covariates. Changes from baseline in HRQL parameters and in performance status will be compared between the treatment groups using the Wilcoxon rank-sum test, considering subjects' disease progression status.

Based on the safety analysis set, information regarding study drug administration, study drug compliance, safety variables, and post-study therapies will be described and summarized. Using data from the pharmacokinetic analysis set, idelalisib plasma concentrations will also be described and summarized.

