### Interim Efficacy Analyses

Two formal interim efficacy analyses for PFS are planned. The first interim analysis will be performed when ~50% of the planned 129 events occur. The second interim will be performed when ~75% of the expected events occur. Type I error rate for testing PFS will be controlled by using the O'Brien-Fleming boundaries. Based on the planned number of PFS events (50% and 75%) for the 2 interim analyses, the 2-sided alpha for the interim and the final analyses are 0.003, 0.018, 0.044. The significant levels will be recalculated based on the actual observed number of events at the time of the interim and final analyses.

---

This study will be conducted in accordance with the guidelines of Good Clinical Practice (GCP), including archiving of essential documents.

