## 7.5. Definitions of Tumor Response and Progression

Responses will be categorized by the IRC as CR, PR, SD, or PD. In addition, a response category of not evaluable (NE) is provided for situations in which there is inadequate information to otherwise categorize response status. A response category of no disease (ND) is included for situations in which there is absence of tumor both at baseline and on treatment.

The best overall response will be determined. The best overall response is the best response recorded from the start of treatment until progressive disease/recurrence (taking as reference for PD the smallest measurements recorded since treatment started). BOR of CR or PR needs to be maintained at least 8 weeks to confirm a response. Subjects who initially responded but did not have an evaluable follow-up visit or did not maintain a response (i.e. progressed) for at least 8 weeks will not be counted as a confirmed responder. Subjects with a best overall response of NE or ND will be counted in the denominators in calculations of tumor response rates. Where imaging data are available, these data will supersede physical examination data in determining tumor status.

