#### 9.4.1.3. Categorical Endpoints

Differences between Arms A and B for ORR, CR and PR rates, nodal response rate, splenomegaly response rate, hepatomegaly response rate, ALC response rate, platelet response rate, hemoglobin response rate, and neutrophil response rate will be compared using Cochran-Mantel-Haenszel Chi-square tests for association between treatment and response, after adjusting for stratification factors. In the analyses of ORR, subjects who do not have sufficient baseline or on-study tumor assessment to characterize response will be counted as failures. For all analyses, odds ratios and the corresponding 95% CIs will be presented.

The potential influence of subject baseline characteristics and of treatment on response rates will be explored with logistic regression modeling.

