## **9.6. Timing of Analyses**

### **9.6.1. Interim Analysis**

The DMC will have access to serious adverse events requiring expedited reporting and will be provided with accumulating safety data on a regular basis. An interim safety review will be conducted by the DMC at ~6 months after the first subject is enrolled. Thereafter, interim safety reviews will be performed by the DMC at intervals of ~6 months; the specific frequency of these reviews will depend upon the rate at which the trial is enrolled, the nature of any emerging safety signals, and monitoring recommendations from the DMC. At each review, all available safety data will be summarized and evaluated.

Two formal interim efficacy analyses for PFS are planned. The first interim analysis will be performed when ~50% of the expected 129 events occur. The second interim will be performed when ~75% of the expected events occur. Type I error rate for testing PFS will be controlled by using the O'Brien-Fleming boundaries. Based on the planned number of PFS events for the 2 interim analyses, the 2-sided alpha for the interim and the final analyses are (0.003, 0.018, 0.044). The significant levels will be recalculated based on the actual observed number of events at the time of the interim and final analyses.

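### Confirmed ORR, the first gate of the secondary chain, can be tested at an early PFS interim, when over a third of randomised subjects cannot yet have a confirming scan

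*Protocol*

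**What the plan says.** **Timing and order.** The synopsis (Statistical Methods) says that the five secondary endpoints are "tested at the 2-sided 0.03 significance level in the order listed at an interim or final analysis when the primary endpoint is rejected". ORR is first there and first in section 9.4.1.6. The synopsis adds: "If a null hypothesis is not rejected, formal sequential testing will be stopped and only nominal significance will be cited for the remaining secondary endpoints". No retest is described.

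**Looks.** Section 9.6.1: "The first interim analysis will be performed when ~50% of the expected 129 events occur". The synopsis: "The second interim will be performed when ~75% of the expected events occur", and "the 2-sided alpha for the interim and the final analyses are 0.003, 0.018, 0.044".

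**Definition.** Sections 3.4.1 and 7.5 require a CR or PR to last at least 8 weeks. Scans fall at Weeks 8, 16, 24, 36 and 48, then every 12 weeks. Section 3.5.1 names two confirming pairs: Week 8 then Week 16, or Week 16 then Week 24.

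**Missing confirmation.** Section 7.5 does not count as confirmed responders "Subjects who initially responded but did not have an evaluable follow-up visit or did not maintain a response" for 8 weeks. For ORR, section 9.4.1.3 says "subjects who do not have sufficient baseline or on-study tumor assessment to characterize response will be counted as failures". Section 9.3.1.1 keeps subjects with a best response of NE or ND in the ITT denominator.

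**The concern.** Together these rules treat a subject who has not yet been scanned in the same way as one who did not respond. At the final analysis this does no harm, because everyone has had time for both scans. At an interim triggered by PFS events it does: recently randomised subjects enter the ORR denominator with no chance of entering the numerator.

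ORR and CR rate are then understated in both arms and the difference between arms shrinks. Because ORR is the first gate, a non-rejection caused by short follow-up would stop formal testing of lymph node response, OS, PFS in the 17p/TP53 subgroup and CR rate. The earlier PFS is rejected, the less mature the ORR gate is.

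**Working it through.** **Inputs from the protocol** (synopsis and section 9.5): 170 + 85 = 255 subjects; half accrued in months 0-7.2 and half in months 7.2-12; exponential PFS with medians of 14 and 8 months; 10% lost to follow-up (taken as exponential over 18 months, also tried as none and as 10% over 12 months); 129 events; looks at 50% and 75%.

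**1. Reproducing the plan's figures.** Schoenfeld: events = (1.960 + 1.036)² / [(2/9) × (ln HR)²] = 128 at HR 0.57 and 130 at 8/14. The power of 129 events is 0.853 or 0.850. O'Brien-Fleming-type spending at 50/75/100% gives 0.0031, 0.0183 and 0.0440, as stated. Under the design alternative PFS is rejected at the first interim with probability about 0.20 and at the second with about 0.40.

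**2. Calendar time of each look.** Expected events at month t are Σ n_k ∫ a(u) · λ_k/(λ_k+η) · [1 − exp(−(λ_k+η)(t−u))] du, with a(u) = 0.5/7.2 up to month 7.2 and 0.5/4.8 from then to month 12. Solving for 64.5 and 96.75 events gives t = 11.86 and 15.09 months. The 129th event falls at about 18.7 to 19.6 months.

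**3. Subjects short of the scans.** The accrual rate is 255 × 0.5/7.2 = 17.7 per month, then 255 × 0.5/4.8 = 26.6 per month. Week 16 is 3.68 months and Week 24 is 5.52 months.
- First interim: randomised = 255 × (0.5 + 0.5 × 4.66/4.8) = 251. Short of Week 16: 26.56 × 3.68 = 98 (39%). Short of Week 24: 26.56 × 4.66 + 17.7 × 0.86 = 139 (55%).
- Second interim: all 255 randomised. Short of Week 16: 26.56 × 0.59 = 16 (6%). Short of Week 24: 26.56 × 2.43 = 64.5 (25%).

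Using the schedule's visit days (Day 106 and Day 162) instead of full weeks, and simulating the event times, gives 36% and 53%, then 6% and 23%. Over both conventions and the dropout variants:

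| Look | Short of Week 16 | Short of Week 24 |
|---|---|---|
| First interim | 36-39% | 53-56% |
| Second interim | 5-9% | 23-28% |
| Final | about 0% | about 0% |

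**4. Effect on the ORR test (illustrative).** The protocol states no ORR assumption. Arm A is set at 76% (the Phase 1 combination study in section 1.3.5.2.2) and Arm B at 58% or 47% (the ofatumumab Phase 2 trial in section 1.1). It is assumed that 70% of responders are first seen at Week 8 and 30% at Week 16.
- Share of responders already confirmed at the first interim: 0.7 × 0.64 + 0.3 × 0.47 = 0.59.
- Measured ORR: 0.76 × 0.59 = 45%, against 0.58 × 0.59 = 34% or 0.47 × 0.59 = 28%.
- Power at 2-sided 0.03 (critical z = 2.17, about 164 v 82 subjects): 28-30% or 66-67%. With full follow-up (170 v 85): 78% or 99%.
- Second interim: share confirmed 0.7 × 0.94 + 0.3 × 0.77 = 0.89; power about 62% or 95%.

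**5. Average loss over the looks.** 0.20 × (78 − 30) + 0.40 × (78 − 62) = 16 percentage points with Arm B at 58%. 0.20 × (99 − 66) + 0.40 × (99 − 95) = 8 points with Arm B at 47%.

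**The case against.** Several points against the concern stand.

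- A reader might infer that half of the subjects at the first interim and a quarter at the second are all scored as failures merely because of the calendar. The protocol does not support that. Those shares apply only if Week 24 is required of everyone, and section 3.5.1 allows confirmation at Week 16. Of the 139 subjects short of Week 24 at the first interim, 139 − 98 = 41 are already past Week 16 and can be confirmed responders. About 20 of the 139 have progressed or died.
- Lymph node response needs no 8-week confirmation. Only subjects without a first post-baseline scan are affected.
- The ORR rates come from a 21-subject single-arm study read by investigators and from refractory populations in another trial, and the 70/30 split has no source.
- Power was not computed conditional on PFS rejection. Rejecting at 0.003 with about 65 events needs an observed hazard ratio near 0.46, and trials with that result may also show larger response differences.
- The shares depend on accrual and effect. With uniform accrual over 9 to 24 months, 22-34% are short of Week 16 at the first interim and 0-20% at the second. With a 20-month Arm A median the figures are 28-31% and 0%.
- Section 9.4.1.2 plans an ORR analysis without confirmation. It is a sensitivity analysis, does not carry the gate, and cannot help subjects who have had no scan.

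It can also be said that interim data-cut conventions belong in the SAP, which was not available here. That would answer a mere omission. Here the protocol itself fixes the time of the test, the denominator, the failure rule and the stopping rule, and their combination causes the loss.

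**Conclusion.** The concern holds in this limited form. The stated rules let confirmed ORR be tested at a first interim where about 36-39% of randomised subjects cannot yet be confirmed responders. In the illustration this cuts ORR power from 78% to about 30%, or from 99% to about 66%. The design gives that path a probability of about 20%. At the second interim (about 40%) the effect is modest, and at the final analysis it is absent.

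Two stronger conclusions are not supported. Type I error is not inflated, because randomisation makes the dilution about equal in both arms, and the PFS conclusion is untouched. Nor does an early PFS win usually close the chain: of the four interim scenarios computed, ORR power is below one half only at the first interim with Arm B at 58%.

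The follow-up shares rest on the protocol's accrual and PFS assumptions. The power figures rest on borrowed response rates and the assumed 70/30 split, so they show the order of the loss and are not a forecast. The change is worth making, and it should be made before any interim result is seen.

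**What to change.** State in the synopsis and section 9.4.1.6 that, if PFS is rejected at an interim, the confirmatory ORR and CR tests use all ITT subjects randomised early enough to have passed a pre-specified confirming scan (Week 24, or at least Week 16, plus visit window) at the data cut. Selection should be by randomisation date only, so that the randomised comparison is kept and early progressors, deaths and dropouts remain in the denominator. Report the full-ITT rate alongside.

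The cost is a smaller interim sample with the Week 24 rule: about 115 subjects at the first interim and 194 at the second. Responses already confirmed at Week 16 in later subjects are set aside for the test. Even so, power at the first interim rises to about 43% (Arm B 58%) or 81% (Arm B 47%).

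Alternatively, keep the PFS decision at the interim and run the secondary chain once, in all ITT subjects, when the last one randomised has passed Week 24. This restores full-follow-up power. It adds an analysis time point and delays the secondary tests, including OS. With accrual ending at month 12 and 5.5 months to Week 24, the delay is 17.5 − 11.9 = about 5.5 months after the first interim, or 17.5 − 15.1 = about 2.5 months after the second.
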